4.5.5 Subgroup Analyses

The different subgroups that will be used for subgroup analyses are described in detail within [Section 4.4.3.3](#)

The primary endpoint will be repeated for all agreed subgroups in [Section 4.4.3.3](#), as well as linear regression analysis using site spirometry data.

ILD/IPF diagnosis summary table, time from enrollment to diagnosis and time to treatment start (from enrollment and from diagnosis) will be reproduced by community/tertiary sites subgroup. Moreover, time from enrollment to diagnosis will be also presented by patients having/not having lung biopsy.

In addition, disease relevant optional assessments summary table will be created by community/tertiary sites subgroup and by country.

In an additional analysis it will be investigated if a FVC decline after three months can predict the annual decline in FVC for individual patients. In the publication from Russell et al. (2016) it is stated that “three-month rate of change predicts disease progression at 1 year”. This analysis will be performed for patients diagnosed with IPF or non-IPF ILD having a minimum of 1 year of observation time, i.e. patients with daily measurements collected for at least 1 year after baseline. The estimated 3 monthly decline and annual decline will be plotted and a Pearson’s correlation coefficient will be calculated. This analysis will be presented in the final analysis of the study.

For progressing and non-progressing patients, patients requiring respiratory-related hospitalizations and the different ILD subgroups, baseline characteristic tables (demographics, medical history, time to first IPF/ILD diagnosis and duration of pre- and post-diagnosis periods) will be repeated for the final analysis.

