4.2.2 Baseline Observations

After discussion of the results of the first interim analysis from December 2018 with the SC in January 2019 it was decided to re-define the calculation for baseline FVC from home spirometry and steps per day from accelerometry. This new definition is given in Table 2 below.

Table 2 Definition of Baseline Observations

	Definition
Baseline data for site visit measurements	Baseline is defined as the measurement collected at the enrollment visit of each assessment.
Baseline data for home measurements	Baseline is defined as the average of the daily measurements collected during the next 7 consecutive days after the first 7 days removed, counted from the day of the first acceptable manoeuvre flagged as 'Good blow' of home spirometry after enrollment visit as defined in Table 1.

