4.4.3.1 Demographics

The following demographic characteristics will be summarized:

- Age (years): date of birth – date of enrollment visit, and age categories (18-64; 65-84; >=85 years)
- Gender
- Race (in case that more than one race will be ticked, a concatenated variable, containing all races will be presented (e.g. Asian/White))
- Ethnicity
- Weight, height and Body Mass Index (BMI) = $\text{weight}(\text{kg})/\text{height}(\text{m})^2$
- Female reproductive status
- Tobacco use history and nicotine exposure
- Alcohol use history and alcohol consumption, that will be presented only in the final analysis.
- Home spirometry and accelerometry : FVC (mL) and steps per day.

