4.4.3.3 Subgroups

In addition, an overview table displaying the number of patients of the different subgroups that are used to investigate exploratory objectives will be given. The table includes the following subgroups:

- Patients from community/tertiary sites
- Countries involved in the study
- Patients with/without post-diagnosis period
- Patients with/without at least 3 months of observation time from first day after the time window for calculation of baseline from home spirometry until EOS

- Patients having/not having at least one lung biopsy
- Progressing/non-progressing patients: progressing patients are characterized by a semi-annual decline in FVC of > 50 ml (using home-based spirometry measurements) and/or >15% decline (absolute difference) in steps/day at the end of the study compared to baseline. The average of the last 7 days measurements will be compared with baseline (defined in Section [4.2.2](#)). Patients not fulfilling these requirements are defined as non-progressing patients. Data up to the end of study visit will be used for the assignment of progressing/non-progressing patients in order to compare the semi-annual FVC decline and steps/day during the whole peri-diagnosis period.
- Patients requiring/not requiring at least one respiratory-related hospitalization (as documented by the investigator in the eCRF)
- ILD subgroups: for non-IPF ILD patients ILD subgroups are defined based on types of ILD as ticked by the investigator in the eCRF, i.e.
 - Collagen = ILD of known causes – Collagen
 - HP = HP (hypersensitivity pneumonitis)
 - NSIP = Idiopathic NSIP: Non-specific interstitial pneumonia
 - uILD = uILD (Unclassifiable ILD)
 - Other = all other types of ILD

In addition to the described baseline characteristics there are several patient population characteristics that are assessed during or at the end of the peri-diagnosis period. These assessments will therefore be analyzed as post-baseline characteristics.

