
 • To further characterize the disease behavior of IPF and non-IPF ILD in the peri-diagnostic period using a multidimensional approach 	
 • Change in pulmonary function (FVC measured in mL and % predicted by site spirometry) • Change in physical functional capacity (measured by daily home accelerometry and site 6-minute walk test [6MWT]) • Change in PRO measures, overall 
 ○ Change in PRO measures during the pre-diagnosis period ○ Changes in PRO measures during the post-diagnosis period • Correlation between home and site spirometry measurements of FVC • Correlation between physical functional capacity assessed at home (by accelerometry) and on site (by 6MWT) • Comparison of disease behavior in IPF and ILD patients • Evaluate the baseline characteristics of progressing vs non-progressing patients, patients requiring respiratory-related hospitalizations • Incidence of non-elective hospitalization, both respiratory and all cause • Incidence of Investigator-reported acute exacerbations ^a • Incidence of death, all cause and respiratory-related deaths • Incidence of events related to the study assessments
Exploratory objectives	

 • Characterization of different subgroups 	
 • Evaluate the characteristics (baseline characteristics, changes in pulmonary function and physical activity) of different ILD subgroups, e.g. connective tissue disease associated ILD, chronic hypersensitivity pneumonitis ILD, etc., depending on available data • Evaluate the characteristics (baseline characteristics, changes in pulmonary function and physical activity) of patients with no diagnosis made 12 months after inclusion into the study

 • Evaluate the differences in FVC values at beginning of treatment, depending on reimbursement restrictions 	
 • Differences in pulmonary function (FVC measured in mL by daily home spirometry and site spirometry) at the start of IPF drug treatment with regards to applicable local reimbursing restrictions for pirfenidone treatment in patients with IPF

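### The baseline week that defines the progressing label is also compared across it, so progressors' displayed baseline steps/day are inflated relative to their true level

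*SAP*

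**What the plan says.** - **Label (SAP 4.4.3.3).** The FVC limb reads "progressing patients are characterized by a semi-annual decline in FVC of > 50 ml (using home-based spirometry measurements". The activity limb is joined to it by "and/or >15% decline (absolute difference) in steps/day at the end of the study compared to baseline". The calculation is that "The average of the last 7 days measurements will be compared with baseline", with a pointer to Section 4.2.2.
- **Baseline (SAP 4.2.2).** For home data, "Baseline is defined as the average of the daily measurements collected during the next 7 consecutive days after the first 7 days removed". After the first interim analysis it was decided to "re-define the calculation for baseline FVC from home spirometry and steps per day from accelerometry", so this single-week definition covers steps.
- **Table content (SAP 4.4.3.1).** The demographic characteristics include "Home spirometry and accelerometry : FVC (mL) and steps per day".
- **Comparison (SAP 4.5.5).** For the final analysis, "baseline characteristic tables (demographics, medical history, time to first IPF/ILD diagnosis and duration of pre- and post-diagnosis periods) will be repeated" by progressing status, among other groupings.
- **Standing of the comparison (SAP Appendix 1, Table 3).** Under a secondary objective: "Evaluate the baseline characteristics of progressing vs non-progressing patients".

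No separate week, correction or caveat is given for the steps/day row.

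**The concern.** A 7-day mean of steps is the patient's usual level plus that week's chance variation. A patient whose baseline week happened to be high is more likely to show a fall of over 15% later, and so to be labelled progressing. The same high value is then printed as that patient's baseline. The reverse holds for a patient whose baseline week was low. The two columns of the table therefore differ on this row for a reason unrelated to disease.

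The comparison is meant to show which baseline features go with progression. Home FVC and steps/day are the only functional measures that the SAP lists for the demographics table, so the steps row is likely to be read for meaning. The problem does not depend on follow-up length or on where the cut is placed, and more patients do not remove it.

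**Working it through.** **Inputs from the SAP.** The cut is 15%, and baseline and final values are each one 7-day mean (4.4.3.3, 4.2.2). For the FVC limb, the mean semi-annual decline is 50 mL with SD 70 mL (2.3). The SAP's only sizing figure reproduces, 1.96 × 70/√72 = 16.17 mL, but it says nothing about steps. Taking declines as normal with mean 50 and SD 70, half of patients exceed 50 mL, so the FVC limb is met with probability 0.5.

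**Assumptions, because the SAP gives no figures.** Mean 5000 steps/day; between-patient log SD 0.4 to 0.6; week-to-week SD of a 7-day mean 10% to 30%; baseline and last-week errors independent; FVC limb independent of steps; no true change in anyone's activity.

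**Hand calculation, error proportional to level.** Let e₁ and e₂ be the log errors of the baseline and last weeks, each with SD s.

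- The steps limb is met if e₂ − e₁ < ln 0.85 = −0.1625. With z = −0.1625/(s√2), its probability is p = Φ(z).
- Given the difference d = e₂ − e₁, the expected baseline error is −d/2. Put a = (s/√2)·φ(z).
- Mean baseline error in progressors (either limb): 0.5a / [p + 0.5(1 − p)].
- Mean baseline error in non-progressors: −a/(1 − p).
- The geometric-mean ratio is the exponential of the difference.

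For s = 0.20: z = −0.575, p = 0.283, φ(z) = 0.338, a = 0.1414 × 0.338 = 0.0478. Progressors: 0.0239/0.641 = +0.0373. Non-progressors: −0.0478/0.717 = −0.0667. Difference 0.1040; ratio exp(0.1040) = 1.11.

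| Weekly SD | Meet steps limb | Labelled progressing | Ratio, by hand (geometric) | Ratio, simulated (arithmetic means) |
|---|---|---|---|---|
| 10% | 12.5% | 56% | 1.03 | 1.03 |
| 15% | 22% | 61% | 1.07 | 1.07 |
| 20% | 28% | 64% | 1.11 | 1.11–1.12 |
| 30% | 35% | 68% | 1.20 | 1.21 |

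The true-level ratio is 1.00 in every row. At 20% and between-patient log SD 0.6, the simulated means are 5188 against 4656 steps/day, a difference of 532.

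**Other error forms.** I simulated 1,000,000 patients per setting under the full and/or label, with weekly error scaled to 10% to 30% at 5000 steps and both between-patient SDs.

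| Error form | Displayed ratio | True-level ratio | Displayed ÷ true |
|---|---|---|---|
| Proportional to level | 1.03–1.21 | 1.00 | 1.03–1.21 |
| Proportional to square root of level | 0.95–1.15 | 0.92–0.97 | 1.03–1.18 |
| Constant in steps | 0.91–1.12 | 0.87–0.95 | 1.03–1.18 |

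The inflation over the true-level ratio appears in all three. The true-level ratio falls below 1 in the last two because patients with low step counts cross a relative 15% cut more often by chance.

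**Effect of a separate week.** If the label's reference week has independent error, the displayed ratio equals the true-level ratio: 1.00 with proportional error, 0.87 to 0.97 otherwise. If that week is adjacent and its error correlates 0.5 with the displayed week (an assumption), proportional error still leaves about 4%, 5% and 10% at weekly SD 15%, 20% and 30%, roughly half of the present 7%, 11% and 21%.

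**Ambiguity in the cut.** The steps criterion is a percentage but carries the words absolute difference. Read as a fixed count, 15% of 5000 = 750 steps, the steps limb alone gave an excess of 12% to 67% in the settings run.

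**The case against.** The case against is substantial, and most of it limits the claim without removing it.

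- **Direction.** A reader might infer that the table will show progressors as more active at baseline. The documents do not support that. It follows only if weekly error is roughly proportional to level, and the SAP does not say how error behaves. With error constant in steps, the displayed ratio with no true change runs from 0.91 to 1.12.
- **Reversal of a real relation.** A reader might also infer that the row will reverse a true link between low activity and progression. That can be constructed with chosen values, but nothing in the SAP supplies them.
- **Steps limb alone.** With proportional error the excess is 14% to 41% if the steps criterion is taken by itself. That is not the SAP's label, which is and/or with FVC.
- **Precision.** At a weekly SD of 20% with proportional error, the 2.5–97.5% sampling range of the ratio is 0.88 to 1.40 with 162 patients (72 IPF plus 90 non-IPF ILD) and 0.80 to 1.59 with 72. The artefact is about one sampling SD. This stands, but sampling error shrinks with more patients and the bias does not.
- **Consequence.** This is one row of a descriptive table in a hypothesis-generating study. No test is planned on it, and age, sex, smoking, medical history and period lengths are not computed from the baseline steps week. This stands and keeps the point modest.

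What survives is that the shared week can be read directly from the SAP, and the row is biased relative to true levels under every error form tried.

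**Conclusion.** The concern holds in a limited form. The steps/day row of the progressing/non-progressing table compares the same weekly mean that sets the label, which inflates the progressor/non-progressor ratio over its true-level value. The size is about 3% to 21% under the full and/or label with no true change, for an assumed week-to-week SD of 10% to 30%, independent errors and an FVC limb met by half of patients. The net sign of the displayed difference is not determined by the documents. The point is confined to steps/day; no size is claimed for home FVC. The primary estimate in the IPF cohort does not use the label and is unaffected. It should be corrected before the final analysis, but it does not threaten the study's main result.

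**What to change.** In SAP Sections 4.4.3.3 and 4.5.5, stop showing steps/day across this label from the week that enters the label. Either:

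1. Keep the existing baseline week as the displayed characteristic and take the label's steps reference from a later week, preferably not adjacent and not overlapping the last 7 days; or
2. Leave the label alone and drop the steps/day row from this one comparison, or footnote it as not interpretable because it enters the label.

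With the second option in particular, show enrollment measures that are already collected and do not enter the label: site FVC, 6MWT distance where performed, mMRC and K-BILD. In the same edit, state whether the 15% is relative to the patient's baseline or a fixed count.

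**Cost.** The first option needs one more derived mean. Patients without data in the reference week lose the steps part of the label, and some patients change group wherever the label is used, including the subgroup repeat of the primary endpoint. It also departs, for this label, from the home baseline re-defined after the first interim analysis. It removes the shared-week bias only so far as the two weeks' errors are independent, and it does not remove chance selection of less active patients by a relative cut. The second option costs only wording and table rows.

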4.6 PHARMACOKINETIC AND PHARMACODYNAMIC ANALYSES

Not applicable.

4.7 SAFETY ANALYSES

4.7.1 Safety Endpoints

The following safety endpoints will be analyzed descriptively by diagnosis cohorts:

- **Non-elective hospitalization, both respiratory and all cause:** a listing and a frequency table will be provided displaying number of patients with at least one non-elective hospitalization, the number of non-elective hospitalizations, the number of patients with at least one respiratory-related non-elective

hospitalization and the number of respiratory-related non-elective hospitalizations during pre- or post-diagnosis periods by diagnosis cohorts.

- **Investigator-reported acute exacerbations:** a listing and a frequency table will be provided displaying number of patients with at least one acute exacerbation and number of acute exacerbations during pre- and post-diagnosis periods by diagnosis cohorts. Additionally, number of patients and events will be given separately for triggered and idiopathic acute exacerbations. Acute exacerbation are defined as per Collard et al. 2016: answering No to the eCRF question “Is there an extra-parenchymal cause identified?”; and answering Yes to the eCRF question “Are there new, bilateral GGO (Ground glass opacification)/ consolidation on CT?” Please refer to [Appendix 8](#) for further information.
- **Death, all cause and respiratory-related:** a listing and a frequency table is given including number of deaths during pre- and post-diagnosis period, primary cause of death and frequencies with respect to autopsies performed.
- **Events related to the study assessments:** documented events will be coded with MedDRA version 21.1 or a higher one. Frequencies of events will be displayed by System Organ Class (SOC) and Preferred Terms (PT) by diagnosis cohorts. In addition, summary of the events characteristics, events by intensity and leading to study discontinuation will be presented separately. The tables will be provided for events occurring during the peri-diagnosis period. If the start date of an event is after or on the day of the enrollment visit or it is ongoing at enrollment visit and the end date of the event is after the day of the initial diagnosis visit, the event belongs to the peri-diagnosis period. A listing with all events will be also presented.

If for any of the above mentioned events an incidence rate of more than 15% is observed, time to event analyses according to the method of Kaplan-Meier will additionally be provided.

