4. STATISTICAL METHODS

Categorical data will be summarized using frequencies and percentages (including a category for missing, if appropriate). Percentages will be based on the number of patients in each diagnosis cohort (a definition of different diagnosis cohorts is provided in Section 4.2.2), if not otherwise specified.

Continuous endpoints will be summarized using descriptive statistics (mean, standard deviation, minimum, 25th and 75th quartiles, median, and maximum).

Where applicable other analysis methods will be specified below.

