4.2.5 End of Study

For individual patients, the end of the study will be as follows:

- Should no diagnosis be made 12 months after inclusion into the study, the patient will leave the study and perform the end of study visit
- Patients diagnosed with a non-ILD condition will leave the study on the date of diagnosis

- Patients diagnosed with IPF or non-IPF ILD will remain in the study and be followed up to the start of drug treatment (within six months) or a maximum of six months if no drug treatment is prescribed

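### Hospitalisations, exacerbations and deaths are planned as crude counts and percentages, so contrasts between periods and between cohorts are confounded with time at risk

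*SAP*

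**What the plan says.** SAP section 4.7.1 opens with "The following safety endpoints will be analyzed descriptively by diagnosis cohorts". Three of the outputs that follow matter here.

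- Hospitalisation: patients with at least one event and numbers of events, ending with "hospitalization and the number of respiratory-related non-elective hospitalizations during pre- or post-diagnosis periods by diagnosis cohorts".
- Acute exacerbation: patients with at least one event and the "number of acute exacerbations during pre- and post-diagnosis periods by diagnosis cohorts".
- Death: "a listing and a frequency table is given including number of deaths during pre- and post-diagnosis period".

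The general rule in section 4 is "Percentages will be based on the number of patients in each diagnosis cohort", unless something else is specified; 4.7.1 specifies nothing else.

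The only analysis of these events that uses time is conditional. Kaplan-Meier is added if "an incidence rate of more than 15% is observed". The section does not say whether the 15% applies per cohort, per period or overall, and it gives no time origin or censoring rule.

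Follow-up is set in sections 4.2.3 to 4.2.5. Before diagnosis it is capped at 12 months. After diagnosis it is capped at 6 months for IPF and non-IPF ILD and stops earlier if drug treatment starts. For the rest, "Patients diagnosed with a non-ILD condition will leave the study on the date of diagnosis", and undiagnosed patients leave at 12 months. Section 4.4.3.4 plans a separate summary table of the lengths of the two periods.

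Table 3 in Appendix 1 lists the incidence of hospitalisation, exacerbation and death among the endpoints of a secondary objective, alongside a comparison of disease behaviour in IPF and ILD.

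**The concern.** A percentage of cohort size treats a patient observed for a few weeks and one observed for the whole period as equally informative. The event tables are laid out by cohort and by period, and time at risk varies along both. A reader of an incidence endpoint will compare the columns, and the tables as planned offer no way to separate a difference in risk from a difference in observation time.

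The SAP adjusts for time elsewhere. The primary endpoint is scaled to 183 days (section 4.5.1), and time to treatment start has Kaplan-Meier estimates with stated censoring (section 4.4.3.4). The event endpoints are the exception. The 15% trigger does not close the gap, because the proportion that opens it also grows with follow-up.

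**Working it through.** **Inputs from the SAP.** Maximum time at risk is 12 months before diagnosis (4.2.3) and 6 months after it (4.2.4). The trigger is 15% (4.7.1). Expected numbers are 72 IPF, 90 non-IPF ILD and about 18 non-ILD or undiagnosed patients, 180 in total (2.3). The SAP states no event rate, no distribution of follow-up and no precision for these endpoints, so there is no figure of its own to reproduce.

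**Assumption.** A constant rate λ per patient-year, identical in both periods, with λ from 0.05 to 0.30 for illustration. Every patient is followed to the maximum of the period.

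**Step 1: share with at least one event.** p = 1 − exp(−λt), with t = 1 year and t = 0.5 year.

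| λ per patient-year | 12 months | 6 months | Ratio |
|---|---|---|---|
| 0.05 | 4.9% | 2.5% | 2.0 |
| 0.10 | 9.5% | 4.9% | 2.0 |
| 0.20 | 18.1% | 9.5% | 1.9 |
| 0.30 | 25.9% | 13.9% | 1.9 |

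For example, at λ = 0.20: 1 − exp(−0.20) = 18.1% and 1 − exp(−0.10) = 9.5%. The rate is the same in both columns, yet the percentage roughly halves.

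**Step 2: the reverse case.** A true two-fold difference can disappear. A rate of 0.20 over 6 months and a rate of 0.10 over 12 months both give 1 − exp(−0.10) = 9.5%.

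**Step 3: the trigger.** The rate at which the crude proportion reaches 15% is λ = −ln(0.85)/t, with −ln(0.85) = 0.1625.

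| Follow-up | Rate needed per patient-year |
|---|---|
| 3 months | 0.1625/0.25 = 0.65 |
| 6 months | 0.1625/0.5 = 0.33 |
| 12 months | 0.1625/1 = 0.16 |
| 18 months | 0.1625/1.5 = 0.11 |

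The same event can pass the trigger before diagnosis and miss it after diagnosis at an unchanged rate: λ = 0.20 gives 18.1% and 9.5%.

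**Step 4: the unit of the trigger.** The count that exceeds 15% depends on the group to which it is applied: 11 of 72 (15.3%), 14 of 90 (15.6%), 3 of 18 (16.7%), or 28 of 180 (15.6%). The SAP does not say which is meant.

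**The case against.** The strongest reply has five parts.

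1. **The two large cohorts share one follow-up rule.** IPF and non-IPF ILD, about 162 of 180 patients (72 + 90), both have up to 12 months before diagnosis and then follow-up to treatment start or 6 months. The cohorts whose rule differs amount to about 18 patients. This stands. Between the two main cohorts the confounding arises only if realised times to diagnosis or treatment differ; it is built in between periods and for the small cohorts.

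2. **The analysis is descriptive, in a study meant for hypothesis generation and estimation.** True, and no test of these events is planned. The issue is therefore interpretability, not error rates. A description that mixes risk with observation time is still hard to read.

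3. **Period lengths are tabulated in section 4.4.3.4.** A reader could form approximate rates from mean durations and event counts. That helps, but the table is not linked to the event tables, gives no interval and does not stop time at a first event.

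4. **The size depends on assumed rates.** It does. The ratio of about 2 changes little over 0.05 to 0.30, but whether 15% is crossed depends on the rate: at 0.10 the crude share is only 13.9% even at 18 months.

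5. **A careless repair could do harm.** Cohorts are defined by a later diagnosis, so a patient must normally survive to diagnosis to count as IPF or non-IPF ILD. Cohort-specific death rates before diagnosis, or Kaplan-Meier curves from enrollment by cohort, would contain immortal time. Plain Poisson intervals on all hospitalisations would ignore repeat events within a patient. This stands and shapes the fix.

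A reader might go further and infer that differences mainly reflect follow-up, that the tables will rank cohorts by length of observation, or that the incidences cannot be quoted at all. The SAP does not support this, since it gives no event rates and no follow-up by cohort. Nor does a range from days to 18 months apply to these tables: 18 months is the maximum for the whole study, the tabulated periods have maxima of 12 and 6 months, and no minimum is stated.

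**Conclusion.** The point holds as one of confounding with time at risk. Section 4.7.1 gives counts and percentages of cohort size for events observed over periods that differ in length by design, and the only time-based analysis is conditional on a crude proportion with the same weakness. At the two period maxima, and under an equal constant rate of 0.05 to 0.30 per patient-year, the percentages differ about 2-fold with no difference in risk. That figure rests on an assumed rate and on full follow-up in both periods; earlier treatment start would shorten the second period, and earlier diagnosis the first. The primary endpoint is not affected. This is an inexpensive improvement to secondary and safety outputs.

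**What to change.** Amend section 4.7.1 as follows.

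- **Hospitalisation (all and respiratory) and acute exacerbation:** beside the counts, show patient-years at risk and patients with a first event per patient-year, with exact 95% confidence intervals, by cohort and period. If total events are also given as rates, use an interval that allows for repeat events within a patient.
- **Death:** give the pre-diagnosis rate over all enrolled patients pooled. Give cohort-specific rates only from diagnosis onward.
- **Kaplan-Meier:** replace the 15% condition with planned estimates, from enrollment for all patients pooled and from diagnosis by cohort for IPF and non-IPF ILD. Censor at treatment start or end of study, and note that censoring at treatment start may be informative.

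The cost is a denominator, a rate and an interval per table plus a fixed set of curves. The period dates are already needed to derive the period lengths in sections 4.2.3 and 4.2.4, so no new data collection is required; the downside is a little more analysis work.
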